4.6 IMMUNOGENICITY ANALYSIS

The immunogenicity analysis will be performed on the safety population.

The anti-atezolizumab antibodies (ADAs) status at baseline will be summarized.

In addition, the incidence of treatment-emergent ADAs will be summarized overall, for all patients with an ADA result from at least one post-baseline sample.

The overall ADAs status will be reported in 4 categories:

- Negative
 - patient with negative or missing ADA result at baseline and always negative post-baseline
- Negative (Treatment unaffected)
 - patient with positive ADA at baseline and always negative post-baseline
 - patient with positive ADA at baseline and treatment unaffected, i.e. with all post-baseline titer results <0.6 compared to baseline titer
- Positive (Treatment enhanced)
 - patient with positive ADA and treatment enhanced, defined as at least one post-baseline titer result ≥ 0.6 compared to patient's baseline titer
- Positive (Treatment induced)
 - patient with negative or missing ADA result at baseline and at least one positive post-baseline

A patient is considered positive if a titer value > 0 is reported.

4.7 SAFETY ANALYSES

Safety will be assessed through summaries of AEs, exposure to Atezolizumab, changes in laboratory test results as well as changes in vital signs and ECGs. The safety variables will be summarized for the safety population. Unless stated otherwise, all safety variables will be summarized for each cohort separately.

4.7.1 Exposure to Study Medication

Number of infusions will be summarized by descriptive statistics. Time on treatment (last dose date minus first dose date, plus 1, expressed in weeks), and total dose received will be summarized.

Missed treatment cycles are not recorded as such in the eCRF (sequential visits are labelled with sequential cycle number regardless of length of time between visits). Therefore to capture “missed doses” and delayed dose irregularities we categorize

- *Patients with one or more missed cycle* as being patients who have ≥ 42 days between two consecutively labelled cycles (target cycle time being 21 days)
- *Patients with at least one cycle delayed by 10 days or more* (i.e. ≥ 31 days between two consecutively labelled cycles). Patients with one or more missed cycle as just defined are also included in this category.

We also present total patient years of exposure to Atezolizumab (per cohort, and across the study) calculated as the sum of individual time on treatment (last day of treatment minus first day of treatment plus one day), expressed in years (i.e. days/365.25).

4.7.2 Adverse Events

Adverse events (AE) will be coded using MedDRA.

AEs will be graded according to the National Cancer Institute Common Terminology Criteria for Adverse Events (NCI CTCAE), Version 4.0. For events of varying severity, the most severe grade as documented on the eCRF will be used in the summaries.

The analysis will focus on treatment-emergent AEs – AEs which start on or after the date of first dose of study drug. (For the assignment of ‘treatment-emergent’ in case of incomplete dates being recorded on the CRF, see Section 4.8.)

AEs of Special Interest are defined according to current Roche global guidelines, and are identified in the clinical database. (This classification overrides the flag set in the eCRF by the Investigator.)

An overview that summarizes the number of patients with treatment-emergent AEs (and the number of events) will be provided including all AEs, related AEs, AEs of Special Interest (AESI), Serious AEs (SAEs), related SAEs, SAEs leading to death, related SAEs leading to death and AEs leading to treatment discontinuation. The number of patients experiencing AEs at each grade (by highest grade) and related AEs at each grade (by highest grade) will also be included.

The number and frequency of patients with treatment-emergent AEs will be presented by primary System Organ Class (SOC) and Preferred Term (PT) within SOC, both overall and for highest grade within patient, for the following:

- All AEs

- Related AEs [“All combined” only]
- AESIs (by AESI class and PT rather than by SOC and PT) [“All combined” only]
- SAEs [“All combined” only]
- Related SAEs [“All combined” only]
- SAEs leading to death [“All combined” only]
- Related SAEs leading to death [“All combined” only]

In addition, a summary of non-serious AEs occurring in 5% or more of patients will be provided (for regulatory disclosure purposes), for “All combined” only.

Patient listings will be provided for:

- AEs leading to treatment discontinuation or interruption
- AESIs
- SAEs
- All deaths.

4.7.3 Laboratory Data

Laboratory data will be analysis for “All combined” only. Hematology and chemistry laboratory data will be summarized in tables presenting the shift from baseline grade to worst NCI CTCAE grade recorded on treatment. Laboratory data recorded at an unscheduled visit (if on treatment) will be included in the calculation of worst grade for the shift tables.

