6.2.2 Rules for Stage II

A study treatment will be considered to be promising for a given cohort in Stage II if:

- there is no unacceptable toxicity, and
- at 18 weeks, there are 8 or more patients with non-progressive disease out of 25 fully-evaluable patients.

If the overall patient population does not meet the Stage II criteria, but a clinical benefit is observed in a specific subgroup (e.g. biomarker positive subgroup) of patients, then Stage II may be expanded to include additional patients from this specific subgroup in order to re-evaluate the Stage II criteria in this patient subgroup.

Additionally, other efficacy endpoints and safety may also be evaluated for a final decision at the end of Stage II.

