6.4 SUMMARIES OF TREATMENT GROUP COMPARABILITY

This is an open-label phase 2 study that will assess Atezolizumab administered at a single dosage (1200 mg q3w). Consequently, no formal treatment group comparability analyses will be conducted. Demographics and medical history will be summarized for each cohort.

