6.6 SAFETY ANALYSES

The safety variables will be summarized for the safety population. All safety variables will be summarized for each cohort.

Safety will be assessed through summaries of AEs, changes in laboratory test results, changes in vital signs and ECGs, and exposure to Atezolizumab.

Verbatim descriptions of AEs will be mapped to thesaurus terms. Adverse event data will be listed by cohort, study site, patient number and study day. Events occurring on or after treatment on Day 1 will be summarized by mapped term, appropriate thesaurus levels, and NCI CTCAE v4.0 grade. In addition, SAEs, deaths, and AESIs will be listed separately and summarized. AEs leading to treatment discontinuation will be listed.

Relevant laboratory and vital signs data will be displayed by time, with NCI CTCAE Grade 3 and 4 values identified, where appropriate. Additionally, all laboratory data will be summarized by grade with use of NCI CTCAE v4.0.

Number of cycles and duration on study medication will be summarized by means of frequency tables and descriptive statistics for continuous variable (N, median, inter-quartile range, mean, SD, minimum, maximum).

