4.3 SUMMARIES OF TREATMENT GROUP COMPARABILITY

This is a single arm study and, consequently, no formal treatment group comparisons will be conducted. Demographics (age, sex, ethnicity, and race) and disease history will be summarized. Medical history, prior and concomitant therapies data will be summarized for “All combined” only.

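### The SAP pools laboratory, vital sign, ECG, most AE-term and prior-therapy summaries over all cohorts, against Protocol 6.4 and 6.6 and without a stated reason

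*SAP*

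**What the plan says.** Protocol 6.6 sets the scope: "Safety will be assessed through summaries of AEs, changes in laboratory test results, changes in vital signs and ECGs, and exposure to Atezolizumab". It then sets the level: "All safety variables will be summarized for each cohort". Protocol 6.4 treats baseline description the same way: "Demographics and medical history will be summarized for each cohort".

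SAP 4.7 opens with a qualified form of that rule: "Unless stated otherwise, all safety variables will be summarized for each cohort separately". It then uses the qualification widely.

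- **Laboratory (SAP 4.7.3):** "Laboratory data will be analysis for “All combined” only".
- **Vital signs and ECG (SAP 4.7.4):** by-visit summaries for the pooled set only.
- **AE term tables (SAP 4.7.2):** pooled only for related AEs, AESIs, SAEs, related SAEs, fatal SAEs and related fatal SAEs.
- **Baseline (SAP 4.3):** "Medical history, prior and concomitant therapies data will be summarized for" the pooled set only.

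The Stage II rule (Protocol 6.2.2, repeated in SAP 3) has two conditions for each cohort. The first is "there is no unacceptable toxicity, and"; the second is at least 8 non-progressors among 25 evaluable patients.

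**The concern.** The trial's conclusions are drawn cohort by cohort, and one of the two conditions for calling a cohort promising concerns toxicity. Neither document defines unacceptable toxicity numerically, so the judgement depends on whatever safety evidence is tabulated for that cohort. The Protocol promises that evidence at cohort level for every safety variable. The SAP withdraws part of it and does not say why.

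Two things are at stake. The first is a cohort-level view of laboratory change from baseline, in groups whose starting values may differ. Protocol 4.1.1, for example, allows transaminases up to 5 times the upper limit of normal with liver involvement, against 2.5 times otherwise. The second is interpretation of the efficacy result. An uncontrolled non-progression rate judged against a fixed 20% is hard to read without the cohort's prior treatment. Eligibility allows either at least one prior systemic line, or none where no therapy known to prolong survival exists.

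**Working it through.** **1. The plan's own figure.** The toxicity condition carries no number. The efficacy condition beside it does: 10% type I error and 80% power. For the rule of stopping at 2 or fewer of 12 and calling 8 or more of 25 promising, the probability of success is the sum over x = 3 to 12 of P(X1 = x) × P(X2 ≥ 8 − x), with X1 binomial(12, p) and X2 binomial(13, p).

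- p = 0.20 gives 0.0991.
- p = 0.40 gives 0.8151.

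Both stated figures are reproduced, and nothing below changes them.

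**2. Level of each output, Protocol against SAP.**

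| Output | Protocol | SAP |
|---|---|---|
| Exposure | by cohort (6.6) | by cohort (4.7.1) |
| AE overview counts | by cohort (6.6) | by cohort (4.7.2, no restriction) |
| All-AE term table, by highest grade | by cohort (6.6) | by cohort (4.7.2) |
| Related-AE, AESI and four SAE term tables | by cohort (6.6) | pooled only (4.7.2) |
| Laboratory shift tables | by cohort (6.6) | pooled only (4.7.3) |
| Vital signs, ECG | by cohort (6.6) | pooled only (4.7.4) |
| Demographics | by cohort (6.4) | by cohort (4.3) |
| Disease history | not named in 6.4 | by cohort (4.3) |
| Medical history | by cohort (6.4) | pooled only (4.3) |
| Prior therapies | by cohort, by inference (6.4 with 4.5.2) | pooled only (4.3) |

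Of the seven AE term tables listed in SAP 4.7.2, 1 runs by cohort and 7 − 1 = 6 are pooled only. The prior-therapy row is an inference: Protocol 6.4 names medical history, and Protocol 4.5.2 places prior cancer therapies within it.

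**3. What stays visible by cohort.** The overview counts patients with any AE, related AEs, AESIs, SAEs and fatal SAEs, down to "related SAEs leading to death" and AEs leading to discontinuation. It also counts patients by highest grade. The all-AE table gives terms by highest grade. Patient listings of SAEs, AESIs, deaths and AEs leading to discontinuation or interruption carry no pooled-only restriction.

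**4. What does not.** Protocol 5.3.5.4 requires a laboratory change from baseline to be reported as an AE if it is symptomatic, changes study treatment, needs intervention or altered concomitant therapy, or is clinically significant in the investigator's judgement. It adds that some abnormal values in oncology trials may not qualify. A change meeting none of these criteria need not enter any AE output. For such values the SAP specifies one output, the pooled shift table. SAP 4 speaks generally of data appearing in listings, but no laboratory listing is among those specified in SAP 4.7.2, and the SAP history records that most listings were removed.

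**5. Weight of one cohort in a pooled table.** With about 725 planned patients (Protocol 9.4), a full cohort contributes 25/725 = 3.4% and a Stage I-only cohort 12/725 = 1.7%. Protocol 3.1 lists 32 groups when sub-cohorts are counted separately. A pooled table therefore does not describe any single cohort.

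**The case against.** The strongest reply has four parts.

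**The restriction is deliberate and disclosed.** SAP 2.2.1 says some analyses are run only on the pooled set, and SAP 4.7 allows exceptions. This stands as far as it goes: the SAP is consistent with itself. It does not reconcile the SAP with Protocol 6.4 and 6.6, which allow no exception.

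**Serious toxicity is still seen by cohort.** This stands, and it limits the point. A reader might infer that a cohort-specific laboratory toxicity would be lost in the pool. The documents do not support that. Appendix 8, for example, has a Grade 3 or 4 hepatic event lead to permanent discontinuation. A laboratory change with that consequence must be reported as an AE under Protocol 5.3.5.4. It would then appear in the cohort's all-AE table by grade, its overview and the discontinuation listing. What stays hidden is mainly change that altered nothing and was judged not clinically significant, which is weak evidence of unacceptable toxicity. With 12 to 25 patients per cohort, the SAE and AESI listings also give term-level detail.

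**Stage I has its own safety review.** SAP 2.3 provides a subset agreed with the Steering Committee. That subset could include laboratory data by cohort, but its content is not specified.

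**Some added tables would be thin.** ECGs after screening are done only when clinically indicated (Appendix 1, note 11), so by-visit ECG tables per cohort would be nearly empty. The shift tables cover haematology and chemistry, whereas Protocol 4.5.6 lists thyroid tests separately, so rerunning them by cohort adds nothing on thyroid function. Precision is low too: 0 events in 25 patients leaves an exact 95% upper limit of 13.7%, and 5 in 25 gives 6.8% to 40.7%. These facts argue for descriptive use and a selective fix, not for leaving the conflict unexplained.

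**Conclusion.** The conflict between the documents holds. Several safety summaries and the medical history and prior-therapy summaries are pooled only, where the Protocol requires cohort level, and no reason is recorded.

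The practical loss is moderate and has three parts:

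- laboratory changes not reported as AEs, with no cohort table or specified listing;
- tabulated AESI and SAE terms by cohort, for which only counts and listings remain;
- prior treatment by cohort, next to the non-progression rate it helps to interpret.

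The toxicity condition can still be judged by cohort in most respects that matter clinically. The documents do not show that any cohort's verdict would change, or that it would be taken from pooled tables. This conclusion assumes that AE reporting follows Protocol 5.3.5.4, and that unrestricted SAP outputs run by cohort under the default in SAP 4.7.

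**What to change.** Remove the pooled-only restriction from the laboratory shift table (SAP 4.7.3), the AESI and SAE term tables (SAP 4.7.2), and medical history with prior therapies (SAP 4.3). Each should run by cohort as well as pooled, at least for cohorts that reach analysis.

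For by-visit vital signs and ECG (SAP 4.7.4), either run them by cohort or record the departure from Protocol 6.6 with a reason. The related-AE term table needs the same choice, because Protocol 6.6 covers it too.

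The cost is more output pages with small denominators. The existing programs can be rerun with cohort as a grouping variable. No new data are needed, and sample size, type I error and power do not change.

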4.7.4 Vital Signs and ECG

Vital signs and ECG data will be summarized by visit (for vital signs, by timepoint within visit) and presented together with change from baseline, for “All combined” only.

4.8 BIOMARKER ANALYSIS

Status of PD-L1 immune cells (IC) and tumor cells (TC) expression will be summarized at baseline, on both efficacy and safety populations. The following categories will be used:

- IC
 - IC0: <1%
 - IC1: 1%-<5%
 - IC2: 5%-<10%
 - IC3: $\geq 10\%$
- TC
 - TC0: <1%
 - TC1: 1%-<5%

- TC2: 5%-<50%
- TC3: $\geq 50\%$

In addition, box plots displaying the baseline PD-L1 continuous IC and TC values will be provided by NPR status at Week 18 (Yes/No), for the efficacy population.

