6.8 EXPLORATORY ANALYSES

Exploratory biomarker analyses (e.g. but not limited to protein and genetic markers) in tumor and plasma samples (both baseline and on treatment) will be performed in an effort to understand the association of these markers with study drug response.

Biomarkers will be summarized using descriptive statistics: N, medians, inter-quartile range, mean, standard deviation, minimum and maximum for continuous variables and frequency counts and percentages for categorical variables. The relationship between biomarkers and efficacy variables will be assessed using appropriate models. More details will be provided in the Statistical Analysis Plan.

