2.1 OBJECTIVES

Efficacy Objectives

The primary efficacy objective for this study is as follows:

To evaluate non-progression rate (NPR) at 18 weeks in patients with advanced solid tumors treated with Atezolizumab, defined as the percentage of patients with complete response (CR) partial response (PR) or stable disease (SD) as assessed by the Investigator¹. The secondary efficacy objectives for this study are as follows:

- To evaluate NPR at 24 weeks, overall response rate (ORR), best overall response (BOR), clinical benefit rate (CBR), duration of response (DOR), time to tumor progression (TTP) and progression-free survival (PFS), as assessed by the Investigator¹.
- To evaluate NPR at 18 and 24 weeks, ORR, BOR, CBR, DOR, TTP and PFS, as assessed by the Investigator using *modified RECIST*²
- To evaluate overall survival (OS)

Safety Objectives

The safety objectives for this study are as follows:

- To evaluate the safety and tolerability of Atezolizumab in patients with advanced solid tumors
- To characterize the immunogenic potential of Atezolizumab by measuring anti-Atezolizumab antibodies and to explore the potential relationship of the immunogenicity response with safety and efficacy

Pharmacokinetic Objectives

The pharmacokinetic (PK) objectives for this study are as follows:

¹ That is, using disease progression status as recorded in the clinical database. Investigator assessments are carried out according to Response Evaluation Criteria In Solid Tumors, Version 1.1 (RECIST, v1.1) (except for prostate cancer and malignant pleural mesothelioma) and disease-specific criteria for patients with prostate cancer (see Protocol Appendix 6) and malignant pleural mesothelioma (see Protocol Appendix 7).

² That is, using disease progression status as recorded in the clinical database, for Investigator assessments carried out according to *modified RECIST* criteria as defined in Protocol Appendix 3.

- To characterize the pharmacokinetics of Atezolizumab

Exploratory Objectives

The exploratory objectives for this study are as follows:

- To evaluate the relationship between tumor tissue PD-L1 expression and measures of efficacy, including NPR at 18 weeks and 24 weeks, ORR, BOR, CBR, DOR, TTP, PFS and OS
- To assess predictive and prognostic exploratory biomarkers(e.g. but not limited to protein and genetic markers on DNA and RNA) in archival and/or fresh tumor tissue and plasma and their association with disease status and/or response to study treatment

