2.2.1 Definition of Cohorts and Extensions/Expansions

Statistical analyses will be based on patients with the same individual tumor type in the protocol-defined cohorts stated in section 2 above. The cohort for each patient will be identified from the data recorded on the “Cohort Assignment” CRF record.

If, during the conduct of the study, a specific subgroup of patients in a cohort is identified, the cohort may be modified to include only that specific subgroup, and then statistical analysis may be performed based on this subgroup of patients. Subgroups of cohorts will be identified by first selecting patients in the appropriate cohort(s), and then filtering for patients meeting the required subgroup criteria.

[figure not shown]
Additionally, a subgroup that applies across multiple tumor types (e.g. a biomarker positive subgroup) may be identified to be of interest.

Cohorts of these latter types will be analyzed using the same methods as for the protocol-defined cohorts.

Statistical analyses will be performed as well on all patients from all cohorts combined. The “All combined” cohort will be analyzed using the same methods as for the protocol-defined cohorts, but won’t include the following analyses: demographics, by-patient plots, time-to-event analyses, PK, immunogenicity and biomarkers. Some of the analyses will be performed only for “All combined” (as specified throughout the SAP).

The enrollment pattern across Stage I and Stage II is shown in Figure 1 below.

Figure 1 Sample Size for Each Cohort in Stage I/II

NP = non-progressors; NPR = non-progression rate.

Assumptions: H_0 = NPR 20%; H_1 = NPR 40%; power = 80%; alpha = 10%.

The sample size was estimated using Simon's optimal two-stage design (Simon 1989).

* And no additional clinical benefit in a subgroup.

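### As planned, the exploratory PD-L1 objective yields no effect estimate or interval: SAP 4.8 gives only per-cohort box plots where Protocol 6.8 promised models

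*SAP*

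**What the plan says.** The objective appears in Protocol 2.4 and again in SAP 2.1: "To evaluate the relationship between tumor tissue PD-L1 expression and measures of efficacy, including NPR at 18 weeks and 24 weeks, ORR, BOR", followed by CBR, DOR, TTP, PFS and OS. That is nine efficacy measures.

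Protocol 6.8 commits to a type of method, "The relationship between biomarkers and efficacy variables will be assessed using appropriate models", and defers the specification: "More details will be provided in the Statistical Analysis Plan".

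SAP 4.8 is where that specification would sit. It has two outputs:
- IC and TC "expression will be summarized at baseline, on both efficacy and safety populations". This is a frequency table of categories IC0–IC3 and TC0–TC3 and is not related to any outcome.
- For the efficacy set, "box plots displaying the baseline PD-L1 continuous IC and TC values will be provided by NPR status at Week 18 (Yes/No".

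SAP 2.2.1 then says that the All combined cohort "won’t include the following analyses: demographics, by-patient plots, time-to-event analyses, PK, immunogenicity and biomarkers". The plots are therefore made cohort by cohort.

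Neither document names a separate PD-L1 plan. The SAP history records the PD-L1 analysis as an addition in version 4.0, so Section 4.8 appears to be its intended home.

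**The concern.** An objective about a relationship needs at least a measure of that relationship with its uncertainty. A box plot by outcome status gives neither, and the method that the protocol promised does not reappear in the SAP.

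The question is open on the protocol's own evidence. In the NSCLC patients described in Protocol 1.3.2, ORR was 26.5% (95% CI 14.3–43.6) with IC of at least 5% and 15.9% (7.2–29.0) below 5%. The 24-week PFS rate ran the other way: 36.4% (19.95–52.74) and 41.1% (26.18–56.07). All these intervals overlap. PD-L1 may therefore relate differently to response and to non-progression, and small plots of Week 18 status alone will not show this.

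The data to do better will exist. Tissue is an entry requirement for every patient, PD-L1 is measured centrally, and Protocol 3.3.2 admits all expression levels. Under SAP Section 4, cohorts that do not reach 12 eligible and evaluable patients are not analysed on their own. With biomarkers also left out of the pooled analysis, the PD-L1 values of those patients have no assured place in any planned comparison with outcome.

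**Working it through.** **1. The plan's own figure.** The documents give no power or precision for the PD-L1 objective. The figure that sets cohort size is the Simon design: 12 patients at Stage I, stop at 2 or fewer non-progressors; 25 in total, success at 8 or more; NPR 20% against 40%, type I error 10%, power 80%. The rejection probability is

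Σ (x = 3 to 12) P(X = x)·P(Y ≥ 8 − x), with X ~ Bin(12, p) and Y ~ Bin(13, p).

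It is 0.0991 at p = 0.20 and 0.815 at p = 0.40, so the design reproduces. It sizes a one-sample test of NPR and not a comparison by PD-L1.

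**2. Objective against output.** Of the nine measures, one (NPR at Week 18) is set against PD-L1, by plot only. None has an estimate, interval, test or model.

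**3. One cohort.** Assumptions, none of them in the documents: 30% IC2/3, NPR 25% in IC0/1, two-sided 5% test. SE(log OR) = √(1/a + 1/b + 1/c + 1/d) from expected cells; power = Φ(z − 1.96) + Φ(−z − 1.96), with z = ln(OR)/SE.

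- OR 3, n = 25. The odds in IC2/3 are 3 × 1/3 = 1, so NPR is 50%. Cells: 3.75, 3.75, 4.375, 13.125. SE = √0.838 = 0.92; z = 1.0986/0.9155 = 1.20; power 22%.
- OR 2, n = 25. NPR in IC2/3 is 40%. Cells: 3, 4.5, 4.375, 13.125. SE = √0.860 = 0.93; z = 0.6931/0.9275 = 0.75; power 12%.

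The cells are small, so these are approximations. Fisher's exact test at n = 25, for NPR 40% against 20% with 5, 8 or 12 PD-L1-high patients, has 11–16% power. A cohort stopped at Stage I has about 12 patients and does worse: for the same contrast, with 20–50% PD-L1-high, the normal approximation gives 11–12% at n = 12 and 18–19% at n = 25.

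**4. The contrast that the box plot draws.** With 8 non-progressors and 17 others, the mean difference detectable with 80% power is about 1.25 SD. An AUC of 0.65 would have a 95% half-width of about 0.24, so it could not be told apart from 0.5.

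**5. Pooled across cohorts.** Assume 400 patients with PD-L1 data (the planned total is about 725). Treated as one 2×2 table, the SE shrinks by √(25/400) = 0.25:

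- OR 3: SE 0.23, z = 4.80, power 99.8%.
- OR 2: SE 0.23, z = 2.99, power 85%.

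These are upper figures, because they ignore stratification. Simulation of the cohort-stratified Mantel-Haenszel test with about 350–400 patients in cohorts of 12 and 25 gives:

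| Odds ratio | Cohorts alike | IC2/3 share and NPR vary between cohorts |
|---|---|---|
| 2 | about 82% | about 66–76% |
| 3 | 97% or more | 97% or more |

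Type I error stayed at about 5%. In the least favourable setting (IC2/3 share 5–60%, NPR in IC0/1 12% or 38%) the SE for OR 2 was about 0.30. Missing PD-L1 values would lower these figures further.

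**6. Range over pooled size.** For NPR 40% against 20% with 20–50% PD-L1-high, unstratified power is 92–98% at 348 patients (29 × 12) and over 99% at 725. For 30% against 20% at 725 it is 72–88%.

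**The case against.** **The objective is exploratory.** It carries no hypothesis, power or error rate, and no primary or secondary result, stopping rule or safety output depends on it. This stands, and it keeps the point minor.

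**The data remain.** A reader might infer that the trial cannot answer the PD-L1 question. The documents do not support that. A pooled model can still be fitted later, but it would not be pre-specified. The gap is in the analysis as planned.

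**Subgroup expansion.** A reader might also infer that cohorts could be expanded in a biomarker-positive subgroup without an estimate to decide on. The documents do not support this either. Protocol 6.2.1 and 6.2.2 rest expansion on benefit observed in the subgroup. SAP Section 3 provides summary statistics and confidence intervals for such subgroups, with 8 of 25 as an informal guide. The rule does not use a positive-versus-negative contrast, and a pooled table at the Final Analysis would come after those decisions. Expansion is no reason for the change.

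**Pooling is not wholly closed.** SAP 2.2.1 says that "a subgroup that applies across multiple tumor types (e.g. a biomarker positive subgroup) may be identified to be of interest", to be analysed like a cohort. That route is optional and is not tied to PD-L1. It would give rates in positive patients with no planned comparison with the rest.

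**The remedy is partial.** It covers two of the nine measures, and the method and cut-offs are choices. This stands in part. The IC cut does have a precedent: Protocol 1.2.4.1 reports urothelial cancer by IHC 2/3 against 0/1, and SAP 4.8 already defines the categories.

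**Conclusion.** The mismatch is real: the protocol promises models, and the SAP delivers a baseline table and per-cohort plots with biomarkers kept out of the pooled analysis. As planned, the PD-L1 objective produces no effect estimate or interval.

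The size of the loss rests on assumed prevalence, NPR, odds ratios and number of patients with PD-L1 data. Under those inputs it is the difference between 12–22% power in a full cohort and, in a stratified pooled analysis, about 97% or more for an odds ratio of 3 and roughly 66–82% for an odds ratio of 2. The unstratified 85% for an odds ratio of 2 should not be quoted as the power of the stratified analysis.

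This is a low-cost improvement to an exploratory analysis. It leaves the validity of the trial's main results untouched.

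**What to change.** In SAP 4.8, add one analysis at the Final Analysis, labelled exploratory: the Mantel-Haenszel odds ratio with 95% CI, stratified by cohort, across all cohorts, for
- Week 18 NPR as defined in SAP 4.4.1, and
- confirmed response (BOR of CR or PR as defined in SAP 4.4.3),

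each for IC2/3 against IC0/1 and for TC2/3 against TC0/1. State the number of patients with missing PD-L1. In SAP 2.2.1, lift the biomarker exclusion for this analysis. For the remaining measures in the objective, say that they will not be related to PD-L1 and why the models foreseen in Protocol 6.8 were not carried over.

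The cost is one or two tables from data already collected. The downside is that a common odds ratio across tumor types is assumed. Stratification guards against confounding by cohort, since both PD-L1 level and NPR can differ by tumor type, but it does not test that assumption.
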